Activity Tracker function. The app will display personalized activity summaries, which will be shared with the study PT. The PT will review the progress with participants via four biweekly phone calls and progressively modify their activities. Participants may also contact the PT via email at any time if they have questions. In Months 3-9, participants will continue using the Fitbit/FitViz app and have access to the PT via email, but no biweekly phone calls. The Delayed Intervention Group will receive the full intervention three months later. Both groups will receive a monthly study newsletter during the 9-month period.

Follow-up assessments will be performed at the end of Months 3, 6 and 9. To better understand the reasons people do or do not adopt and maintain recommended levels of physical activity, all participants will be interviewed for one hour by phone after the intervention by a PhD medical sociology trainee. Interviews will focus on 1) goals set, strategies used, barriers/facilitators to being physically active, 2) their experience with the intervention, 3) the nature of activities they engage in, and 4) their experience of being a research participant. These data will enrich the RCT data, and inform the design of the future implementation strategy.

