**Power Calculation:** Our collaboration with PABC, Fraser Health, and patient groups will allow the study to recruit 60 eligible participants within 6 months. For a proof-of-concept study, it is reasonable to expect moderately large difference between groups after the physical activity intervention. In one of our pilot studies involving 27 patients with RA, [name] et al. found an average of 71.8 minutes (SD=96.2) of activities at 3 METs bouted at 10-minute intervals (unpublished data). Assuming an attrition rate of approximately 15%, we anticipate 50 of the 60 participants will complete the study. With a sample size of 50 and  $\alpha$ -level of 0.05, we will have 96.3% power to detect a between-group difference of at least 10 minutes, or 13.9% in the primary outcome measure after the intervention (Appendix C).

**Data Management:** Prior to use, the SenseWear unit will be configured using the participant's handedness, smoking status, age, sex, height and weight and set to collect data in one-minute intervals. All data will be downloaded and processed using the SenseWear Professional™ software (Version 8.1), and stored at the secured server at ARC, which backs up the data every 24 hours. The processed data will then be exported for further processing and data analysis using a customized data analysis protocol developed by [name] using MATLAB® software. Self-reported outcome measures will be administered using the online survey system hosted by ARC. This is a fully encrypted, secure website with 128-bit SSL encryption, which is also used by many major banks. To minimize human error, skip logics for questions and the available range for each variable will be programmed in the online questionnaire. Databases will be created in the Microsoft Excel format, which can be easily converted into SAS, SPSS, and other statistical packages for statistical analysis. We will use multiple imputations to investigate the impact of missing data in the study, although every effort will be used to minimize the amount of missing data.

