**Data Analysis:** Because the aim of a proof-of-concept study is to demonstrate evidence of efficacy, an intention-to-treat analysis will be performed. The main analysis will include the bouted mean moderate/vigorous activity minutes (primary outcome measure), bouted mean sedentary minutes, the KOOS and the Partners in Health Scale. For the main comparison, we will use analysis of covariance (ANCOVA) to compare between the Immediate Intervention Group and Delayed Intervention Group at 3 months, using the baseline measure as a covariate. In addition, ANCOVA will be used to assess the difference between the Intervention Group at 3 months and the Control Group at 6 months, with the baseline measure as a covariate. We anticipate that the two groups should be similar if the delay of 3 months in the Delayed Intervention Group does not influence the effect of the intervention. We will also use repeated measure ANOVA to assess the within group differences over the four assessment periods. No adjustment will be made for multiple comparisons because Type II error is a greater concern than Type I error in proof-of-concept studies. Descriptive analysis will be used to summarize participant characteristics and comorbid conditions.

The literature suggests that physical activity and chronic disease self-management experiences are different for men and women. Although this project is not powered to examine the effect in outcomes for men and women separately, exploratory analysis will be done to assess trends in each group. The results will provide information for a sample size calculation in future studies of online physical activity interventions.

We will also examine the mechanism of the intervention on physical activity participation by conducting mediation analysis using the bootstrapped sampling distribution model by Preacher & Hayes. Changes in Theory of Planned Behaviour variables over the intervention period (i.e., between baseline and 3 months) will be examined as potential mediators on physical activity behaviour after the 3-month intervention.

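### Does the mediation analysis need a named visit, named covariates and a causal caveat, given that beliefs and activity may be measured at the same month-3 visit?

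*Combined protocol and SAP*

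**What the plan says.** The purpose is given in the Data Analysis text of section 4.3: "We will also examine the mechanism of the intervention on physical activity participation by conducting mediation analysis". The method is a bootstrap of the indirect effect. The mediator is change in Theory of Planned Behaviour scores, and its window and the outcome are described as "i.e., between baseline and 3 months) will be examined as potential mediators on physical activity behaviour after the 3-month intervention". The window is fixed for the mediator only. The outcome has no named visit, and the text does not say which activity measure is used, whether it enters as a level or a change, or which covariates are included.

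The main efficacy comparison, earlier in the same subsection, is specified more fully: the arms are compared "at 3 months, using the baseline measure as a covariate".

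Two statements in the Study Procedure bear on timing. "Follow-up assessments will be performed at the end of Months 3, 6 and 9", so nothing is measured between baseline and month 3. "The Delayed Intervention Group will receive the full intervention three months later", so month 3 is the only follow-up with an untreated randomised comparator.

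**The concern.** Mediation is a claim about order: the intervention shifts beliefs, and the shifted beliefs then raise activity. Only the arm is randomised. If belief change and activity are both read at month 3, nothing in the data puts one before the other. Reverse feedback is plausible on the protocol's own theory. Section 2.1 describes perceived behavioural control partly as a person's sense of having the ability to carry out the behaviour, and becoming more active could raise it.

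A later outcome visit exchanges one difficulty for another. Month 6 or 9 activity does follow the belief change, but by then the delayed arm has begun the intervention, and the contrast is early against late start rather than treated against untreated.

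What is at stake is the wording of a secondary result. A reader could take a positive indirect effect as proof that changed beliefs drove activity, and a later trial could be designed on that footing. Leaving visit and covariates open also allows more than one version of the model to be fitted.

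**Working it through.** **Plan's own figure.** There is none to reproduce. The documents give no power, effect size or expected indirect effect for mediation, so the figures below are illustrations on stated assumptions.

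**Inputs from section 4.3 (Power Calculation and Study Procedure).** 50 completers at 1:1 allocation, so 25 per arm. The pilot "found an average of 71.8 minutes (SD=96.2) of activities at 3 METs bouted at 10-minute intervals", and the target is "a between-group difference of at least 10 minutes, or 13.9% in the primary outcome measure after the intervention". Taking both in the same time unit, 10/71.8 = 13.9% and the standardised arm effect is 10/96.2 = 0.104 SD. The same section also says "it is reasonable to expect moderately large difference between groups after the physical activity intervention", which is the reason for trying 0.5 and 0.8 SD as well. On that SD, 0.8 × 96.2 = 77 minutes, more than the pilot mean of 71.8.

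**Assumed model: reverse feedback only, true indirect effect zero.**

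- Activity: Y3 = 0.6·Y0 + d·arm + 0.8·e
- Belief: M3 = 0.6·M0 + g·(Y3 − Y0) + 0.8·e
- Mediator: M3 − M0. Indirect effect: a·b, where a is the arm effect on the mediator and b is the mediator's effect on Y3 given arm.
- Y0, M0 and the errors are independent with unit variance. There are 1,000 trials per setting and 500 percentile-bootstrap resamples each. The Monte Carlo standard error is at most 1.6 percentage points.

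Share of trials with the 95% interval wholly above zero (nominal 2.5%), for g = 0.3 / 0.5 / 0.7:

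| Arm effect d | Adjusted for Y0 | Arm only |
|---|---|---|
| 0.104 SD | 1% / 3% / 6% | 1% / 1% / 2% |
| 0.5 SD | 4% / 13% / 23% | 2% / 4% / 7% |
| 0.8 SD | 5% / 27% / 47% | 1% / 9% / 20% |

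With no path between activity and belief and independent errors, the share is 0.3% or less. The rates are therefore high only when a large arm effect is combined with moderate to strong feedback. The low rates at 0.104 SD partly reflect low power and are not in themselves reassuring. The top-end rates also move with the assumed autocorrelation and noise.

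**Common cause.** Suppose there is no path either way, the arm effect is 0.5 or 0.8 SD on both variables, and the residual correlation is 0.3. After adjustment for baseline activity, 22% and 42% of trials are positive.

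**Different assumptions.** These use arm effects of 0.5 and 0.8 SD, path or common-cause strengths of 0.3 and 0.5, and adjustment for both baseline activity and baseline belief (400 trials per setting):

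| Truth | Adjusted | Unadjusted |
|---|---|---|
| Activity drives belief | 6.5% to 38% | 1.5% to 18% |
| Common cause | 13% to 68% | 2.5% to 29% |
| Belief drives activity | 36% to 90% | 9.5% to 45% |

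The ranges overlap, so a positive interval does not separate the three explanations, with or without covariates.

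**Would naming covariates help?** If belief truly drives activity (path 0.3, arm effect on belief 0.8 SD), adding baseline activity raises power from 39% to 53%. Under change-driven reverse feedback (d = 0.8, g = 0.7), the same step raises false positives from 20% to 47%. If feedback follows the level of activity instead of its change, adjustment makes no difference (46% either way). Neither choice is better throughout.

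**Would naming the visit help?** Month 3 keeps the randomised contrast and loses time order. Month 6 or 9 restores time order and loses the untreated comparator. No assessment in the schedule gives both.

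**The case for a change.** The best case for a change is that it costs two or three sentences and no new data. The plan shows with its ANCOVA that it can name a visit and a covariate, so the gap is specific to this model. The lead sentence speaks of mechanism with no limit on interpretation. Fixing the model beforehand would prevent a choice made after seeing results, and a caveat written in advance binds more firmly than one added at reporting. The interviews do not fill the gap, because they take place after the intervention and cannot show which changed first.

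Much of this stands. The visit, activity variable and covariates are unnamed, and a month-3 indirect effect does not identify direction.

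It does not follow that the plan should be amended. It cannot be stated as fact that both variables cover the same interval, because the text sets the interval for the mediator alone. A caveat offering only two directions would be incomplete, since a common cause can produce the same result. Prescribing baseline activity as the sole covariate would impose a debatable choice, and baseline belief score has a claim too because the mediator is a change score. A better-worded caveat would alter no estimate.

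**Conclusion.** No change is needed. The limitation is real but is inherent in the assessment schedule; naming a visit or adding a covariate does not remove it. The missing detail is of the kind an analyst fills sensibly. Month 3 is the only visit with an untreated comparator, bouted moderate/vigorous activity is the primary measure, and the covariates can be chosen and reported openly as the trade-off they are. The plan calls the belief scores potential mediators and commits to no causal conclusion, so there is no claim to withdraw. The primary month-3 ANCOVA is unaffected.

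On size, reverse feedback alone gave a positive adjusted result in 1% to 6% of simulated trials at the 0.10 SD implied by the protocol's own figures, and in 5% to 47% at 0.8 SD. These rates rest on assumed feedback of 0.3 to 0.7, autocorrelation of 0.6 and 25 completers per arm. None of them is an estimate for this trial. A report of the indirect effect should call it exploratory and compatible with beliefs driving activity, activity driving beliefs, or a shared cause. That is a matter for interpretation when the result is in hand.
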